10.5.1 Introduction

This appendix describes the process to be followed to identify and appropriately report cases of Hy's Law. It is not intended to be a comprehensive guide to the management of elevated liver biochemistries.

During the course of the study, the investigator will remain vigilant for increases in liver biochemistry. The investigator is responsible for determining whether a subject meets potential Hy's Law criteria at any point during the study.

The investigator participates, together with MedImmune clinical project representatives, in review and assessment of cases meeting potential Hy's Law criteria to agree whether Hy's Law criteria are met. Hy's Law criteria are met if there is no alternative explanation for the elevations in liver biochemistry other than drug-induced liver injury (DILI) caused by the investigational product.

The investigator is responsible for recording data pertaining to potential Hy's Law/Hy's Law cases and for reporting AEs and SAEs according to the outcome of the review and assessment in line with standard safety reporting processes.

10.5.2 Definitions

10.5.2.1 Potential Hy's Law

AST or ALT $\geq 3 \times$ ULN **together with** TBL $\geq 2 \times$ ULN at any point during the study following the start of study medication irrespective of an increase in alkaline phosphatase (ALP).

10.5.2.2 Hy's Law

AST or ALT $\geq 3 \times$ ULN **together with** TBL $\geq 2 \times$ ULN, where no other reason, other than the investigational product, can be found to explain the combination of increases; eg, elevated ALP indicating cholestasis, viral hepatitis, or another drug.

For potential Hy's Law and Hy's Law, the elevation in transaminases must precede or be coincident with (ie, on the same day) the elevation in TBL, but there is no specified timeframe within which the elevations in transaminases and TBL must occur.

10.5.3 Identification of Potential Hy's Law Cases

In order to identify cases of potential Hy's Law, it is important to perform a comprehensive review of laboratory data for any subject who meets any of the following identification criteria in isolation or in combination:

- ALT $\geq 3 \times$ ULN
- AST $\geq 3 \times$ ULN
- TBL $\geq 2 \times$ ULN

In cases where a subject may meet any of the abnormal laboratory identification criteria, in isolation or in combination, the central laboratory will immediately send an alert to the investigator (also sent to sponsor study representative).

The investigator will also remain vigilant for any local laboratory reports where the identification criteria are met, where this is the case the investigator will:

- Notify the sponsor study representative
- Request a repeat of the test (new blood draw) by the central laboratory
- Complete the appropriate unscheduled laboratory case report form (CRF) module(s) with the original local laboratory test result

When the identification criteria are met from central or local laboratory results the investigator will without delay:

- Determine whether the subject meets potential Hy's Law criteria (see Section 10.5.2) by reviewing laboratory reports from all previous visits (including both central and local laboratory results)

10.5.4 Follow-up

10.5.4.1 Potential Hy's Law Criteria Not Met

If the subject does not meet potential Hy's Law criteria the investigator will:

- Inform the study representative that the subject has not met potential Hy's Law criteria.
- Perform follow-up on subsequent laboratory results according to the guidance provided in the study protocol.

10.5.4.2 Potential Hy's Law Criteria Met

If the subject does meet potential Hy's Law criteria the investigator will:

- Notify the sponsor study representative who will then inform the study team

The medical monitor contacts the investigator, to provide guidance, discuss and agree an approach for the study subjects' follow-up and the continuous review of data. Subsequent to this contact the investigator will:

- Monitor the subject until liver biochemistry parameters and appropriate clinical symptoms and signs return to normal or baseline levels, or as long as medically indicated
- Investigate the etiology of the event and perform diagnostic investigations as discussed with the medical monitor. This includes deciding which the tests available in the Hy's Law laboratory kit should be used.
- Complete the Liver CRF Modules as information becomes available.
- If at any time (in consultation with the medical monitor) the potential Hy's Law case meets serious criteria, report it as an SAE using standard reporting procedures.

10.5.5 Review and Assessment of Potential Hy's Law Cases

The instructions in this section should be followed for all cases where potential Hy's Law criteria are met.

No later than 3 weeks after the biochemistry abnormality was initially detected, the medical monitor will contact the investigator in order to review available data and agree on whether there is an alternative explanation for meeting potential Hy's Law criteria other than DILI caused by the investigational product. The medical monitor and Global Safety Physician will also be involved in this review together with other subject matter experts as appropriate.

According to the outcome of the review and assessment, the investigator will follow the instructions below.

If there is an agreed alternative explanation for the ALT or AST and TBL elevations, a determination of whether the alternative explanation is an AE will be made and subsequently whether the AE meets the criteria for a SAE:

- If the alternative explanation is **not** an AE, record the alternative explanation on the appropriate CRF
- If the alternative explanation is an AE/SAE, record the AE /SAE in the CRF accordingly and follow the sponsor's standard processes

If it is agreed that there is **no** explanation that would explain the ALT or AST and TBL elevations other than the investigational product:

- Report an SAE (report term ‘Hy’s Law’) according to the sponsor’s standard processes.
 - The ‘Medically Important’ serious criterion should be used if no other serious criteria apply
 - As there is no alternative explanation for the Hy’s Law case, a causality assessment of ‘related’ should be assigned

If, there is an unavoidable delay of over 3 weeks in obtaining the information necessary to assess whether or not the case meets the criteria for Hy’s Law, then it is assumed that there is no alternative explanation until such time as an informed decision can be made:

- Report an SAE (report term ‘Potential Hy’s Law’) applying serious criteria and causality assessment as per above
- Continue follow-up and review according to agreed plan. Once the necessary supplementary information is obtained, repeat the review and assessment to determine whether Hy’s Law criteria are met. Update the SAE report according to the outcome of the review

QRS	ECG interval measured from the onset of the QRS complex to the J point
QT	ECG interval measured from the onset of the QRS complex to the offset of the T-wave
QTc	cardiac QT interval corrected for heart rate
QTcB	cardiac QTc interval corrected for heart rate by the formula of Bazett
QTcF	cardiac QTc interval corrected for heart rate by the formula of Fridericia
RR	The time between corresponding points on 2 consecutive R waves on the ECG
SAE	Serious adverse event
SAP	Statistical analysis plan
SC	Subcutaneous
SOC	MedDRA system organ class
TEAE	Treatment emergent adverse event
TESAE	Treatment emergent serious adverse event
WHO-DD	World Health Organization Drug Dictionary

1 INTRODUCTION

This document describes the statistical analysis for protocol D7870C00002 (Amendment 2, 28Nov2017), a trial of MEDI5884 in a Phase 2a randomized, double-blind, placebo-controlled, parallel-design study to evaluate the safety, PK, pharmacodynamics (PD), and immunogenicity of multiple subcutaneous (SC) doses of MEDI5884 in subjects with stable CHD who are currently receiving high-intensity statin therapy. This document details the statistical summaries relating to each study objective and describes the general conventions and definitions that will be used. In addition, a set of table, listing, and figure templates and specifications is planned to be created in a statistical programming plan (SPP) to complement this document.

2 STUDY OVERVIEW

2.1 Study Objectives

2.1.1 Primary Study Objective(s)

Evaluate the safety and tolerability of repeated [REDACTED] dosing with MEDI5884 in subjects with stable CHD

2.1.2 Secondary Study Objectives

- Establish the PK profile of MEDI5884 following repeat dosing
- Evaluate the effect of MEDI5884 on HDL-C and apoB
- Assess immunogenicity

2.1.3 Exploratory Study Objectives

- [REDACTED]
- [REDACTED]
- [REDACTED]

2.2 Study Design

This is a Phase 2a randomized, double-blind, placebo-controlled, parallel-design study to evaluate the safety, PK, PD, and immunogenicity of multiple SC doses of MEDI5884 in subjects with stable CHD who are currently receiving high-intensity statin therapy. At least 120 subjects are planned to be randomized across approximately 25 study sites in the United States of America to evaluate up to 5 dose levels of MEDI5884 via SC injection ([REDACTED],

[REDACTED] compared to placebo (Figure 2.2-1). Subjects will be dosed once monthly for [REDACTED] and will be randomized in a [REDACTED] ratio to receive MEDI5884 ([REDACTED]) or placebo (volume matched for [REDACTED] MEDI5884). Subjects will be followed for [REDACTED] post last dose (up to [REDACTED]).

Figure 2.2-1 Study Flow Diagram

2.3 Treatment Assignment and Blinding

An (Interactive voice/web response system) IXRS will be used for randomization to a treatment group and assignment of blinded investigational product. A subject is considered randomized into the study when the investigator notifies the IXRS that the subject meets eligibility criteria and the IXRS provides the assignment of blinded investigational product kit numbers to the subject.

Subjects will be randomized in a [REDACTED] ratio to receive MEDI5884 ([REDACTED] [REDACTED]) or placebo (volume matched to [REDACTED] MEDI5884).

[figure not shown]
This is a double-blind study in which MEDI5884 and placebo are visually distinguishable until SC doses are prepared. Neither the subject nor any of the investigator or sponsor staff

who are involved in the treatment or clinical evaluation of the subjects will be aware of the treatment received (ICH E9).

In order to maintain the blind, an unblinded pharmacist will be responsible for dose preparation including preparation of volume matched placebo injections.

Once prepared, MEDI5884 and placebo are indistinguishable. A blinded qualified designee will administer investigational product to subjects via SC injection.

2.4 Sample Size

3 STATISTICAL METHODS

3.1 General Considerations

Data will be provided in listings sorted by treatment group and subject number. Tabular summaries will be presented by treatment group. Categorical data will be summarized by the number and percentage of subjects in each category. Continuous variables will be summarized by descriptive statistics, including mean, standard deviation, median, minimum, and maximum. Baseline values will be defined as the last valid assessment prior to the first administration of investigational product unless otherwise specified.

When last observation carried forward (LOCF) is used to impute for missing post-baseline data, only post-baseline data will be carried forward (e.g., baseline data will not be carried forward).

All statistical tests will be 2-sided at an alpha = 0.05 significance level unless stated otherwise.

Data analyses will be conducted using the SAS® System Version 9.3 or higher (SAS Institute Inc., Cary, NC).

3.2 Analysis Populations

The analysis populations are defined in Table 3.2-1.

Table 3.2-1 Analysis Populations

Population	Description
As-treated population	Subjects who receive any study investigational product will be included in the as-treated population and subjects will be analyzed according to the treatment they actually received.
PK population	Subjects who received any amount of MEDI5884 with at least one detectable post treatment serum concentration measurement
ADA evaluable population	Subjects who have non-missing baseline ADA data and at least one non-missing post-treatment ADA assessment

3.3 Study Subjects

3.3.1 Subject Disposition and Completion Status

A summary of subject eligibility and randomization as well as treatment group received (including summary of subjects randomized but not treated) will be provided. In addition, disposition of subjects throughout the study will be provided with respect to completion of treatment, discontinuation of treatment, and discontinuation of study.

3.3.2 Demographics and Baseline Characteristics

Demographic information related to sex, age, race, weight, height, and body mass index (BMI) will be presented by treatment group and for all subjects combined. A summary of baseline disease characteristics may include, but not be limited to, total cholesterol, HDL-cholesterol, LDL-cholesterol (direct and Friedewald equation), apoB, apoA1, and background statin.

3.3.3 Study Drug Exposure

The number of study drug (investigational product) doses received will be summarized by treatment group.

3.3.4 Concomitant Medications

Concomitant medications (administered during or after treatment) will be coded using the current WHO Drug Dictionary. Concomitant medications will be summarized using frequency count and percentage by the highest anatomical therapeutic chemical (ATC) class and preferred term. All concomitant medications will be presented in a data listing.

3.4 Efficacy Analyses

There are no efficacy endpoints in this study.

3.5 Pharmacodynamic Endpoint(s) and Analyses

All pharmacodynamic analyses will be based on the As-treated population.

3.5.1.1 Secondary Pharmacodynamic Endpoint(s)

- Change in apoB (mg/dL) from baseline to [REDACTED]
- Percent change in HDL-C from baseline to [REDACTED]

3.5.1.2 Analysis of Secondary Pharmacodynamic Endpoint(s)

PD analysis will be based on the As-treated population. The secondary PD endpoints, change from baseline to [REDACTED] in apoB and percent change from baseline to [REDACTED] in HDL-C, will be summarized by treatment group. Statistical comparisons of these endpoints between each MEDI5884 treatment group and placebo will be performed using an analysis of covariance (ANCOVA) by adjusting baseline value and treatment group with last-observation-carried forward (LOCF) approach to handle any missing data. A one-sided upper 95% confidence interval comparing each MEDI5884 treatment group to placebo for change from baseline to [REDACTED] in apoB will be provided. There will be no adjustment for multiple comparisons or multiple endpoints.

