3.2.1 Dose Rationale

[figure not shown]
Doses for this study have been selected based on the preliminary results of PK/PD (Cohorts 1 to 3) data from the ongoing Phase 1 SAD study of MEDI5884 (D7870C00001).

A PK/PD model was developed to describe MEDI5884 PK and the corresponding HDL changes over time using an indirect response model. Model estimates were based on fitting PK/PD data simultaneously in healthy volunteers [REDACTED]
[REDACTED]

MEDI5884 PK appeared nonlinear. A 2 –compartment population PK model with linear and nonlinear clearance described the data of all 3 cohorts well. The estimated PK parameters are presented in [Table 3.2.1-1](#) and [Figure 3.2.1-2](#). 

[figure not shown]

[REDACTED]

[REDACTED]
[REDACTED]
[REDACTED]
[REDACTED]
[REDACTED]

[REDACTED]
[REDACTED]

[REDACTED]
[REDACTED]
[REDACTED]
[REDACTED]
[REDACTED]

In summary, the proposed doses of MEDI5884 in this study are expected to be well tolerated, and the collected PK/PD data will be appropriate to fulfill the objectives of this study. The follow-up duration is sufficient to evaluate the potential immunogenic profile of MEDI5884 and monitor any potential impact on PD markers as a result of neutralizing ADA.

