4.1.7 Replacement of Subject

Subjects who do not complete dosing per randomization for any reason other than for safety (which includes subjects who withdrew due to an AE or by having met withdrawal criteria for withdrawal of investigational product (Section 4.1.6) may be replaced if deemed necessary by the medical monitor to ensure that safety and PK data are collected from a sufficient number of subjects and to maintain the balance of the study.

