4.2.2.1 Early Discontinuation Visit or Unscheduled Study Visit

Study procedures should be completed as per [REDACTED]/early discontinuation visit for subjects who prematurely discontinue from the study and for subjects who require an unscheduled study visit. Subjects should be encouraged to remain in the study for follow-up.

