4.8.6 Pharmacodynamic Analysis

PD analysis will be based on the As-treated Population. The primary PD endpoints, change from Baseline to [REDACTED] in apoB and percent change from Baseline to [REDACTED] in HDL-C, will be summarized by treatment group. Statistical comparisons of these endpoints between each MEDI5884 treatment group and placebo will be performed using an analysis of covariance (ANCOVA) by adjusting baseline value and treatment group with last-observation-carried-forward approach to handle missing data. A one-sided upper 95% confidence interval comparing each MEDI5884 treatment group versus placebo for change from Baseline to [REDACTED] in apoB will be provided.

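### LOCF for missing HDL-C and apoB endpoint values shifts the MEDI5884-minus-placebo contrast if that difference is still changing; a repeated-measures model should be the main analysis

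*SAP*

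**What the plan says.** SAP 3.5.1.2 compares each MEDI5884 group with placebo on change in apoB and percent change in HDL-C by ANCOVA, "by adjusting baseline value and treatment group with last-observation-carried forward (LOCF) approach to handle any missing data". It adds a one-sided upper 95% limit for apoB. Protocol 4.8.6 has the same analysis, "with last-observation-carried-forward approach to handle missing data". SAP 3.1 restricts carrying to post-baseline values but sets no limit on how early the carried value may be. No missing-data assumption, alternative model or sensitivity analysis is visible for these endpoints. SAP 3.5.1.4 and 3.6 cannot be read.

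Several provisions bear on how much is missing:

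- Protocol 4.1.6 keeps subjects who are taken off product in follow-up, including those stopped for an apoB rise.
- Protocol 4.1.5 ends data collection when a subject withdraws from the study.
- Protocol 4.2.2.1 provides an "early discontinuation visit for subjects who prematurely discontinue from the study". Whether it includes lipids is not visible.
- Protocol 4.1.7 says that non-completers of dosing, other than for safety reasons, "may be replaced if deemed necessary by the medical monitor".
- SAP 3.2 keeps every dosed subject in the analysis: "Subjects who receive any study investigational product will be included in the as-treated population".

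**The concern.** LOCF replaces the missing endpoint value with whatever was measured last. SAP 2.2 says "Subjects will be dosed once monthly for" a redacted period, so a value taken after an early dose may stand in for one taken after the full course. The dose rationale (protocol 3.2.1) uses a model to "describe MEDI5884 PK and the corresponding HDL changes over time using an indirect response model", so HDL-C is expected to move with exposure. No apoB time course is visible.

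The secondary hypothesis (protocol 1.7.2) is that HDL-C rises without raising apoB. If the treatment difference is still growing, LOCF errs against the HDL-C effect and towards finding no apoB rise. The second error is the less cautious one, because the upper limit is there to guard against an apoB increase.

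The plan also does not say whether an exit-visit value is the one carried, or how values observed after product is stopped are used.

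**Working it through.** **Inputs.** The cohort table gives 6 x 20 = 120, matching the stated minimum of 120. The sample-size text is not readable, so there is no power, SD or dropout figure to reproduce. Everything else is assumed: three monthly post-baseline lipid visits with the endpoint at the third; half of the leavers lost after visit 1 and half after visit 2; 5, 10 or 20% missing; SD 15; between-visit correlation 0.6; correlation with baseline -0.3.

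**Bias.** Let m be an arm's missing share and g its mean change still to come after the carried visit. LOCF misses the arm mean by -m x g, so the contrast is off by

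-m_active x g_active + m_placebo x g_placebo.

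With equal random leaving this is -m x (g_active - g_placebo): only a change in the difference counts.

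- Shared drift: active 13/17/20, placebo 3/7/10. Both arms have g = [(20-13)+(20-17)]/2 = [(10-3)+(10-7)]/2 = 5, so the bias is 0. Simulation at 20% missing gave 0.04, within simulation error.
- The same drift with 20% missing on active and 5% on placebo: -0.20 x 5 + 0.05 x 5 = -0.75. Shared drift then no longer cancels.

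**Size under equal random leaving**, with e1, e2, e3 the treatment differences at the three visits:

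bias = (m/2) x [(e1-e3) + (e2-e3)]

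- HDL-C 20/35/45: (m/2) x (-25-10) = -17.5m
- apoB 3/7/10: (m/2) x (-7-3) = -5m

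If an exit value midway to the next visit is carried, the factors become (m/2) x [(27.5-45)+(40-45)] = -11.25m and (m/2) x [(5-10)+(8.5-10)] = -3.25m. If every leaver is also replaced, the missing share falls to 1/21, 2/22 or 4/24 = 4.8, 9.1 or 16.7%.

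| Missing | HDL-C, points | HDL-C, exit value | HDL-C, exit value and replacement | apoB, mg/dL | apoB, exit value | apoB, exit value and replacement |
|---|---|---|---|---|---|---|
| 5% | -0.9 | -0.6 | -0.5 | -0.25 | -0.16 | -0.15 |
| 10% | -1.75 | -1.1 | -1.0 | -0.5 | -0.33 | -0.3 |
| 20% | -3.5 | -2.25 | -1.9 | -1.0 | -0.65 | -0.5 |

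**Consequences** (simulated: random leaving, 6 arms of 20, no exit value, 5/10/20% missing). The repeated-measures fit was a maximum-likelihood stand-in for the Kenward-Roger model.

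- HDL-C 95% interval coverage: LOCF 94.8/94.2/90.7%; repeated measures 95.1 to 95.2%.
- HDL-C root mean squared error (RMSE): LOCF 4.73/5.04/5.98; repeated measures 4.64/4.72/4.92.
- apoB upper limit below the true difference (nominal 5%): LOCF 5.5/6.1/7.6%; repeated measures 4.8/4.9/5.0%.
- apoB RMSE: LOCF 4.56/4.58/4.68; repeated measures 4.63/4.71/4.93.

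**Cost in precision.** For constant variance the SE ratio is sqrt(1 + [m/(1-m)] x (1-rho^2)). At rho = 0.6 it is 1.017, 1.035 and 1.077 for 5, 10 and 20% missing. In simulation the SD of the apoB estimate went from 4.56/4.55/4.57 with LOCF to 4.63/4.71/4.93.

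For HDL-C the cost is 0 to about 1.5% if its SD is constant, because LOCF's mixing of visit means inflates its own variance. If the SD grows over time the cost is of the same order as for apoB. A four-visit simulation with SD 12 to 22 gave model SEs of 6.94 to 7.18 (+3.5%) at 10% and 6.90 to 7.46 (+8%) at 20%.

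**Other patterns at 20% missing** (bias, LOCF against repeated measures):

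- apoB difference falling 10/7/3: +1.1 against 0.
- Leaving depends on observed values: rising HDL-C -2.4 against 0; rising apoB about -0.1 for both.
- Leaving depends on unobserved values: rising HDL-C -4.1 against -1.2; rising apoB -1.6 against -1.2; flat difference -0.55 against -1.1, where LOCF does better.

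**The case against.** The strongest counter-case is that little may be missing and the carried gap may be short. Stopping product does not end follow-up, leavers have an exit visit, and some are replaced. The blood-volume table (protocol 4.3.7) lists 14 post-baseline draws before the last three small rows; if many include lipids, the carried value lies close to the endpoint and the monthly-step figures overstate the shift. For apoB, LOCF has the lower RMSE at every rate above, and an HDL-C error from a growing difference is conservative. These are secondary endpoints in a Phase 2a trial whose primary objective is safety, with no visible apoB margin. All of this stands as a limit on size. It does not remove the problem: withdrawal ends data collection, and a dosed subject who is replaced stays in the As-treated population with a carried value.

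A reader might infer more than the documents support:

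- That any continuing change in lipid levels biases the contrast. Under equal random leaving, shared drift cancels.
- That protocol 3.2.1 shows HDL-C still moving at this trial's endpoint. Its model was fitted to single-dose data in healthy volunteers.
- That the plan has no other method at all. Two SAP sections are unreadable, so only the visible text can be judged.
- That the precision cost falls on apoB alone. It also falls on HDL-C if its SD grows over time.

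**Conclusion.** The point holds in conditional form. With LOCF as the only visible method, the contrast is unbiased under equal random leaving only if the treatment difference is constant after the carried visit. If leaving differs by arm or depends on outcome, shared drift can also bias it. Under the assumed growing differences the shift is under 1 HDL-C point and about 0.25 mg/dL apoB at 5% missing (one subject in an arm of 20), and 3.5 points and 1.0 mg/dL at 20%; exit or interim values make it smaller. Against an SE of 15 x sqrt(2/20) = 4.7 this is probably modest.

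The gain is clearest for HDL-C at 10% missing or more with a constant SD. With SD growing 12/17/22, LOCF had slightly lower HDL-C RMSE at 5 to 10% missing and higher RMSE at 20% (7.39 against 7.16). For apoB the gain is a correctly placed upper limit, not a smaller total error. The change is worth making because it is standard and cheap. Confidence is medium, since no dropout rate, SD, endpoint visit or time course is visible.

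**What to change.** Before sponsor personnel are unblinded at the interim analysis (SAP 4), amend SAP 3.5.1.2 and protocol 4.8.6:

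- **Main analysis of both endpoints:** a repeated-measures model with treatment, visit, treatment-by-visit, baseline and baseline-by-visit; unstructured covariance with a stated fallback; Kenward-Roger degrees of freedom. Take the contrast and the one-sided 95% apoB limit at the endpoint visit.
- **Visits:** use the lipid visits already scheduled, once confirmed from the full schedule. If they are too many for an unstructured matrix with about 120 subjects, pre-specify a subset that includes the endpoint visit.
- **State:** the missing-at-random assumption; whether values observed after product is stopped are included; and how early-discontinuation values map to scheduled visits, so that they are not lost.
- **Sensitivity analysis:** keep ANCOVA with LOCF, and state that it assumes a constant treatment difference after the carried visit, with leaving equal across arms and unrelated to outcome.

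The cost is wording and some programming. No new samples appear to be needed: PD samples are scheduled (protocol 4.3.6) and apoB is checked before later doses (protocol 4.1.6), but the lipid rows of the schedule are not visible. The SAP cites Amendment 2 while the protocol is at Amendment 4, so an update is due anyway.

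Downsides to state in the plan: the SD of the estimate rises by about 1 to 2% at 5%, 2 to 5% at 10% and 6 to 10% at 20% missing for apoB, and also for HDL-C if its SD grows over time (0 to about 1.5% if constant). ApoB RMSE is not improved. There is no gain when the treatment difference is constant, and no guaranteed gain when missingness depends on unobserved values.
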